## 8 Data Collection

The research coordinators will collect data and record it either on paper data sheets or in a custom-designed computer database.

## 9 Risk Assessment

This study involves randomization to usual care or PEEP titration by EIT, and then crossover to the other arm. All patients will receive a high PEEP strategy during the usual care arm of the protocol. In addition, mini-BAL will be performed at three time points during the protocol on each subject.

### 9.1 Risks of mini-BAL

Study subjects will be assessed before, during and for 15 minutes after the mini-BAL. Potential complications of the Mini-BAL procedure include pneumothorax, bronchial hemorrhage, vagal reflex, bronchial irritation, and transient arterial hypoxemia. Prior to performing mini-BAL the study subject's FiO2 will be increased to 1.0 ten (10) minutes prior to the start of the procedure. Mini-BAL will not be performed if the P/F ratio is < 100 or the imputed S/F ratio is less than 89. Mini-BAL will not be performed if the platelet count < 50 K/uL. During performance of the mini-BAL the procedure will be terminated for a saturation <89% sustained for greater than 1 minute following the administration of any aliquot. The early termination of the mini-BAL, based on the above criteria, will be reported as an adverse event.

### 9.2 Risks of High PEEP

Historical risks include pneumothorax and hypotension. However, no significant differences in pneumothorax or barotrauma, nor vasopressor use or circulatory and other organ failures were noted in randomized trials save for the ART trial, which used a decremental PEEP approach following an aggressive high pressure, long duration recruitment maneuver. This was felt to be largely accountable to the aggressive recruitment maneuver, which will not be used as part of this protocol.[25] Recruitment maneuvers in both groups (if required in the High-PEEP group during routine management) will be performed in accordance with University of Michigan protocol

(Appendix I). High-PEEP management will also follow our standard University of Michigan guidelines for clinical practice.

### **9.3 Risk of Death**

It is unlikely that one treatment arm may lead to more deaths; mortality will be monitored during the course of the 24-hour study, but is not a clinical outcome of this trial.

### **9.4 Minimization of Risks**

Federal regulations at 45 CFR 46.111(a)(1) require that risks to subjects are minimized by using procedures which are consistent with sound research design. Oxygen saturations and arterial blood gases, if indicated, will be monitored during the mini-BAL procedures. We will use a high PEEP protocol based on those used in multiple large clinical trials, that were shown safe, feasible, and of potential clinical benefit for the intended population or moderate to severe ARDS. The DSMB will be reviewing data as outlined above and will examine not only efficacy but safety (inclusive of mortality) and will reserve the right to halt the study at any time.

### **9.5 Potential Benefits**

Study subjects may or may not receive any direct benefits from their participation in this study. High PEEP has been shown to improve oxygenation in ARDS, to be safe in multiple large trials, and of potential benefit in moderate-severe ARDS. This approach is routinely chosen by most clinicians. Titration of PEEP by EIT, if anything, should be safer than using the customary PEEP table insofar as it provides real time insight into whether lung zones are being over ventilated and manifesting tidal hyperinflation.

### **9.6 Risks in Relation to Anticipated Benefits**

Federal regulations at 45 CFR 46. 111 (a)(2) require that “the risks to subjects are reasonable in relation to anticipated benefits, if any, to subjects, and the importance of the knowledge that may reasonably be expected to result.” Based on the preceding assessment of risks and potential benefits, the risks to subjects are reasonable in relation to anticipated benefits.

**Procedures** – Mini-BAL can result in transient worsening of hypoxemia. This is usually transient in nature. Mini-BAL will not be performed for a P/F ratio  $<100$  or an S/F ratio  $<89$  and will be terminated for a S/F ratio of  $<89$  for more than one minute. Mini-BAL can result in lung irritation and bleeding. Mini-BAL will not be performed if platelets  $< 50$  K/uL.

**Treatments** – High PEEP is routinely used in clinical practice. The EIT belt is noninvasive and minimally discomforting to wear. There is potential for benefit to society and individual patients should EIT prove to be result in less lung inflammation and a large clinical trial were to demonstrate clinical benefit.

# 10 Human Subjects

Each study participant or a legally authorized representative must sign and date an informed consent form. Institutional review board approval will be required before any subject is entered into the study.

## 10.1 Selection of Subjects

### 10.1.1 Equitable Selection of Subjects

Federal regulations at 45 CFR 46(a)(3) require the equitable selection of subjects. The Emergency department and Critical Care Medicine Unit will be screened to determine if any patient meets inclusion and exclusion criteria. Data that have been collected as part of the routine management of the subject will be reviewed to determine eligibility. No protocol-specific tests nor procedures will be performed as part of the screening process. If any subjects meet criteria for study enrollment, then the attending physician will be asked for permission to approach the patient or his/her LAR for informed consent. Study exclusion criteria neither unjustly exclude classes of individuals from participation in the research nor unjustly include classes of individuals from participation in the research. Hence, the recruitment of subjects conforms to the principle of distributive justice.

### 10.1.2 Justification of Including Vulnerable Subjects

The present research aims to investigate the safety and efficacy of a type of treatment for patients with ARDS. Due to the nature of ARDS and its risk factors (e.g., sepsis, trauma), the vast majority of these patients will have impaired decision-making capabilities. This study cannot be conducted if limited to enrolling only those subjects with retained decision-making capacity. Hence, subjects recruited for this trial are not being unfairly burdened with involvement in this research simply because they are easily available.

## 10.2 Informed Consent

Federal regulations 45 CFR 46.111(a)(5) require that informed consent will be sought from each prospective subject or the subject's legally authorized representative (LAR). As we will enroll critically ill, intubated patients, we anticipate almost all consents will be from the subject's LAR, and thus the remainder of this section will focus on LARs. The investigator is responsible for ensuring that the LAR understands the risks and benefits of participating in the study, and answering any questions the LAR may have throughout the study and sharing any new information in a timely manner that may be relevant to the LAR's willingness to continue the subject's participation in the trial. The consenter will make every effort to minimize coercion. All study participants or their LARs will be informed of the objectives of the study and the potential risks. The informed consent document will be used to explain the risks and benefits of study participation to the LAR in simple terms before the patient is entered into the study, and to document that the LAR is satisfied with his or her understanding of the risks and benefits of participating in the study and desires to participate in the study. The investigator is responsible for ensuring that informed consent is given by each LAR. This includes obtaining the

appropriate signatures and dates on the informed consent document prior to the performance of any protocol procedures.

### **10.3 Withdrawal of Consent**

Patients may withdraw or be withdrawn (by the patient or LAR) from the trial at any time without prejudice. Data recorded up to the point of withdrawal will be included in the trial analysis, unless consent to use their data has also been withdrawn.

### **10.4 Identification of Legally Authorized Representatives**

Many of the patients approached for participation in this research protocol will invariably have limitations of decision-making abilities due to their critical illness. Hence, most patients will not be able to provide informed consent. Accordingly, informed consent will be sought from the potential subject's legally authorized representative.

Regarding proxy consent, the existing federal research regulations ('the Common Rule') states at 45 CFR 46.116 that "no investigator may involve a human being as a subject in research...unless the investigator has obtained the legally effective informed consent of the subject or the subject's legally authorized representative"; and defines at 45 CFR 46 102 (c) a legally authorized representative (LAR) as "an individual or judicial or other body authorized under applicable law to consent on behalf of a prospective subject to the subject's participation in the procedures(s) involved in the research." OHRP defined examples of "applicable law" as being state statutes, regulations, case law, or formal opinion of a State Attorney General that addresses the issue of surrogate consent to medical procedures. Such "applicable law" could then be considered as empowering the LAR to provide consent for subject participation in the research.

According to a previous President's Bioethics Committee (National Bioethics Advisory Committee), an investigator should accept as an LAR...a relative or friend of the potential subject who is recognized as an LAR for purposes of clinical decision making under the law of the state where the research takes place (National Bioethics Advisory Committee (NBAC), 1998). Finally, OHRP has opined in their determination letters that a surrogate could serve as a LAR for research decision making if such an individual is authorized under applicable state law to provide consent for the "procedures" involved in the research study (Office of Human Research Protections (OHRP), 2002).

### **10.5 Justification of Surrogate Consent**

According to the Belmont Report, respect for persons incorporates at least two ethical convictions; first, that individuals should be treated as autonomous agents, and second, that person with diminished autonomy are entitled to protection. One method that serves to protect subjects is restrictions on the participation of subjects in research that presents greater than minimal risks. Commentators and Research Ethics Commissions have held the view that it is permissible to include incapable subjects in greater than minimal risk research as long as there is the potential for beneficial effects and that the research presents a balance of risks and expected direct benefits *similar* to that available in the clinical setting (Dresser, 1999). Several U.S. task forces have deemed it is permissible to include incapable subjects in research. For example, the American

College of Physicians' document allows surrogates to consent to research involving incapable subjects only "if the net additional risks of participation are not substantially greater than the risks of standard treatment." (American College of Physicians, 1989). Finally, the National Bioethics Advisory Committee (NBAC) stated that an IRB may approve a protocol that presents greater than minimal risk but offers the prospect of direct medical benefits to the subject, provided that...the potential subject's LAR gives permission..." (National Bioethics Advisory Committee (NBAC), 1998)

Consistent with the above ethical sensibilities regarding the participation of decisionally incapable subjects in research and the previous assessment of risks and benefits in the previous section, the present trial presents a balance of risks and potential direct benefits that is **similar** to that available in the clinical setting, with the exception of the additional blood draws.

## **10.6 Additional Safeguards for Vulnerable Subjects**

The present research will involve subjects who might be vulnerable to coercion or undue influence. As required in 45CFR46.111(b), we recommend that additional safeguards be included to protect the rights and welfare of these subjects. Such safeguards might include, but are not limited to: a) assessment of the potential subject's capacity to provide informed consent, b) requirement for subject's assent, c) the availability of the LAR to monitor the subject's subsequent participation and withdrawal from the study; d) augmented consent processes.

## **10.7 Confidentiality**

Federal regulations at 45 CFR 46 111 (a) (7) requires that when appropriate, there are adequate provisions to protect the privacy of subjects and to maintain the confidentiality of data. To maintain confidentiality, study related data and reports will identify subjects by a coded number only. Only the study research teams will have access to the codes. All records will be kept in a secure password protected computer. All computer entry and networking programs will be done with coded numbers only. All paper case report forms will be maintained in a locked cabinet inside a locked office. Clinical information will not be released without the written permission of the patient.

# **11 Adverse Events**

Assuring patient safety is an essential component of this protocol. Each participating investigator has primary responsibility for the safety of the individual participants under his or her care. The Investigators will determine daily if any clinical adverse experiences occur during the period from enrollment through the end of the protocol, 24 hours after enrollment.

The following adverse events will be collected in the adverse event case report forms:

- Serious adverse events
- Non-serious adverse events that are considered by the investigator to be related to study procedures

- Adverse events that lead to permanent discontinuation of the study procedures

A clinical trial adverse event is any untoward medical event associated with the use of a drug or study procedure in humans, whether or not it is considered related to a drug or study procedure.

If a patient's treatment is discontinued as a result of an adverse event, study site personnel must report the circumstances and data leading to discontinuation of treatment in the adverse event case report forms.

### **Clinical Outcomes**

Routine clinical outcomes of ARDS are exempt from adverse event reporting unless the investigator deems the event to be related to the conduct of study procedures. The following are examples of events that will be considered clinical outcomes:

- Death related to ARDS or a sequela of ARDS based on the interpretation of the investigator.
- Cardiovascular events: the need for vasoactive drugs or fluids for hypotension or hypotension.
- Respiratory events: decreased  $\text{PaO}_2/\text{FiO}_2$ , hypoxia, worsening acute respiratory distress syndrome, or respiratory failure, unless related to performance of the mini-BALs.
- Hepatic events: hepatic injury or liver dysfunction that leads to an increase from baseline in the serum level of bilirubin.
- Renal events: renal failure, renal insufficiency, or renal injury that leads to an increase from baseline in serum creatinine.
- Hematologic/coagulation events: coagulopathy, disseminated intravascular coagulation, thrombocytopenia, or thrombocytosis.
- Systemic inflammatory response syndrome related criteria: tachypnea, tachypnea, leukocytosis, leukopenia, hypothermia, hyperthermia, tachycardia, or bradycardia that does not meet the definition of severe and prolonged.

Note: Arrhythmias such as atrial fibrillation, heart block, ventricular tachycardia or ventricular fibrillation are not considered clinical outcomes and should be recorded as adverse events if they are serious events, are considered by the investigator to be related to study protocol, or lead to discontinuation of the protocol.

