#### PEEP Titration Procedure:

1. The procedure involves two phases: a recruitment phase followed by a gradual reduction in the end-expiratory pressure phase (Decremental PEEP).

2. Recruitment Phase: Pressure control with a drive pressure of 15 cm H2O and PEEP of 20 cm H2O (ie, 35/20) will be applied for 5-10 breaths and then increased to a PEEP of 25 cm H2O (ie, 40/25) for 1 minute.
3. Decremental PEEP: In volume control, VT will be set to 6 mL/kg PBW and PEEP to 20. Every 5-10 minutes, PEEP will be reduced by 2 cm H2O. PEEP will be reduced until one of the following occurs: 1) drop in EELI in any region during the stabilization period by >10%, 2) PEEP = 5 cm H2O, or 3) patient develops hemodynamic instability or SpO2 <88%.
4. The best EIT-PEEP is identified as that which demonstrates the best compromise in over-distension (OD) and collapse (CL), as determined by the ODCL EIT variable.

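### Hypotension, hypoxia and early stops during EIT PEEP titration reach the adverse event form only if judged related (or, arguably, if study procedures end for good), whereas a mini-BAL cut short is always reported

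*Combined protocol and SAP*

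**What the plan says.** Section 11 collects three kinds of event: serious adverse events, "Non-serious adverse events that are considered by the investigator to be related to study procedures", and adverse events that end the study procedures permanently. Under Clinical Outcomes it then takes routine outcomes of ARDS out of reporting. These are "exempt from adverse event reporting unless the investigator deems the event to be related to the conduct of study procedures". The cardiovascular example is "Cardiovascular events: the need for vasoactive drugs or fluids for hypotension or hypotension". The respiratory example covers a fall in P/F, hypoxia, "worsening acute respiratory distress syndrome, or respiratory failure, unless related to performance of the mini-BALs". The serious adverse event definition in the same section excludes anything classified as a clinical outcome.

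Section 5.1.5 (PEEP Titration Procedure, step 3) gives three ways for the decremental PEEP phase to end: a regional fall in EELI, PEEP reaching 5 cm H2O, or "patient develops hemodynamic instability" or an SpO2 below 88%. Step 4 then identifies the best PEEP. No reporting duty is attached to the third ending.

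For the mini-BAL, Section 9.1 says: "The early termination of the mini-BAL, based on the above criteria, will be reported as an adverse event". On high PEEP, Section 9.2 says: "Historical risks include pneumothorax and hypotension". Section 5.0 describes the trial as unblinded.

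**The concern.** The protocol names hypotension as a risk of high PEEP and writes instability and desaturation into the end rule of the titration. Those same events sit on a list that is exempt unless someone who knows which procedure was under way attributes them to it. In patients with P/F below 150, hypotension and hypoxia have a ready alternative explanation in the illness itself, so the attribution is a matter of judgement.

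The sampling procedure is handled more strictly than the experimental one. What is at stake is whether the DSMB, which Section 9.4 asks to examine safety, gets a complete count of titrations that ended for instability or desaturation. Section 9.5 suggests that EIT titration should, if anything, be safer than the table. That count bears directly on the statement.

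**Working it through.** The documents give no figure on this point, so there is nothing to recompute. The check is to trace each route by which an event during EIT titration could reach the adverse event form.

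1. **Non-serious event, judged related (Section 11).** Open. It depends wholly on the investigator's judgement.
2. **Non-serious event, judged unrelated.** Closed. The collection list takes non-serious events only if related, and the clinical-outcome exemption applies as well.
3. **Serious event, judged unrelated.** Closed for hypotension and hypoxia, because the serious adverse event definition excludes clinical outcomes. Open for pneumothorax, which is not on the exempt list, and for serious arrhythmias, which a note under Clinical Outcomes says are to be recorded.
4. **Event that permanently ends study procedures.** Arguably open. The collection list asks for no relatedness judgement here, but Section 11 does not say whether this overrides the exemption. The arrhythmia note grants the route expressly only to events that are not clinical outcomes.
5. **Decremental phase ended for instability or low SpO2.** No route of its own. Step 4 of Section 5.1.5 still selects a PEEP, so such an ending is not on its face a permanent discontinuation.
6. **Mini-BAL ended early.** Always open. Section 9.1 makes the termination itself the reportable event.

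The scheduled data do not fill the gap left by routes 2, 3 and 5. Section 6.3 expects EIT titration to take 20 to 40 minutes and defines time 0 as the moment PEEP is finally established. Heart rate, blood pressure and SpO2 at Hour 0 are recorded after PEEP setting, both in the first period and after crossover. Section 6.3 specifies continuous monitoring only for the mini-BAL. Values during recruitment and the decremental steps are therefore not required data, and the reason a decremental phase ended is not among the items listed in Section 6.3 or Appendix F.

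Exposure: 20 planned patients × 1 EIT titration each (first or after crossover) = 20 titrations.

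**The case against.** **The exemption is conditional.** It covers routine outcomes only, and its relatedness exception applies to every study procedure, EIT titration included. The extra mention of the mini-BAL in the respiratory item largely repeats that general exception. Section 11 also defines an adverse event without regard to relatedness. This stands against any claim that these events are simply unreportable. It does not supply a mandatory route: the definition is broad, but the collection list and the exemption narrow what is recorded.

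**The affected events are not all the main harms of EIT.** Section 9.2 concerns high PEEP, which patients also receive under the table. It names pneumothorax first, and it reports no significant differences in barotrauma or vasopressor use in randomized trials, apart from one whose aggressive recruitment maneuver it says will not be used here. This stands. The point is limited to hypotension and hypoxia.

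**A planned end of a decremental trial is not an aborted procedure.** Section 5.1.5 lists instability or low SpO2 as one of three endings and does not predict that it will occur. Low SpO2 at a reduced PEEP step may only show that the decrement has reached its end. This stands in part. It is a reason to record why each phase ended, so that planned endings and early stops can be told apart.

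**The DSMB may see more than adverse event forms.** Section 11 says it monitors trial data, and Section 6.3 names scheduled vital signs as a basis for assessing safety. That is fair, but those values follow PEEP setting. Appendix I, the recruitment policy, is on file and not reproduced, so a recording rule in it cannot be excluded.

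**Size.** A reader might infer that a given share of events will be missed. The documents give neither a rate of stopped titrations nor a share that would be judged unrelated. The nearest statement is in Appendix E, where an observational study of 39 ARDS patients reports no complications with its titration trials. Its maneuver differed and complications are not defined, so it does not settle the rate.

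**Conclusion.** The point holds for hypotension (including vasoactive drugs or fluids given for it), for hypoxia, and for decremental phases ended for instability or SpO2 below 88%. The first two reach the form only through an unblinded relatedness judgement or, arguably, permanent discontinuation. The last has no mandatory route, although an early-terminated mini-BAL has one. Following the protocol as written can leave these events unrecorded, so this is more than a missing detail.

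The documents do not support the stronger reading that the principal harms of EIT titration are hidden from the DSMB. Pneumothorax and serious arrhythmias remain reportable, a conscientious investigator may report the rest, and the DSMB is not confined to adverse event forms.

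No number of missed events can be given. What can be said is that the gap applies to all 20 planned EIT titrations. The conclusion assumes that Appendix I contains no recording rule that closes it. The change is a low-cost improvement to the safety data. The efficacy comparison is not affected.

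**What to change.** Add the following to Section 11 and the case report form. It concerns recording only; the stop rule and every threshold in Section 5.1.5 stay as they are.

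- Record the reason each decremental phase ended.
- Record any recruitment or decremental phase ended early for hemodynamic instability or desaturation, and report it to the DSMB regardless of judged cause, as Section 9.1 does for the mini-BAL. Recruitment must be named separately, because the third ending in step 3 belongs to the decremental phase only.
- Record new or increased vasopressor or fluid treatment for hypotension, and desaturation, over one defined window around PEEP setting. Use the same window for EIT and for the High-PEEP table; otherwise EIT would be the only method under close observation.
- Tabulate for the DSMB by PEEP method and period. Both randomized sequences receive EIT, so a table by randomized arm would mix the two methods.

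The cost is a short addition to Section 11, an addition to the case report form for each PEEP setting, and a few more forms. Some of these will reflect the underlying illness or a planned end of the decrement. Recording the reason for ending lets the DSMB identify the planned endings.
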